12.9.6. Safety Figures

Safety: Figures					
No.	Population	IDSL / Example Shell	Title	Programming Notes	Deliverable [Priority]
Haematology					
3.1.	Safety	SAFE_F1	Subject Profiles for Haematology by Treatment Group	
By Haematology parameter.
 
This output should be produced for:
 
Platelet Count, Haemoglobin
 
Use rules for CTCAE boundaries
 
X axis use 'Actual Relative Time (Days)' from dose. Show all observed values including unscheduled.
 
Add footnote "Figure displays a subset of haematology parameters"
 
Panel by treatment group
	SAC
3.2.	Safety	SAFE_F2	Mean Profile for Haematology by Treatment Group	
By Haematology parameter.
 
This output should be produced for:
 
Platelet Count, Haemoglobin
 
X axis shows visits with approximate temporal spacing
 
Add footnote "Figure displays a subset of haematology parameters"
	SAC
3.3.	Safety	SAFE_F3	LFT Patient Profiles	
ALT = Alanine Amino Transferase, AST = Aspartate Amino Transferase, Alk. Phos. = Alkaline Phosphatase, Total Bili. = Total Bilirubin
	SAC
ECG					
3.4.	Safety	EG7	Empirical Distribution Function for Maximum Change from baseline in QTcF Interval	Both treatments in one plot. Calculate maximum change from baseline.	SAC

CONFIDENTIAL

208564

Safety: Figures					
No.	Population	IDSL / Example Shell	Title	Programming Notes	Deliverable [Priority]
3.5.	Safety	EG8	Distribution of QTcF Change by Visit and Treatment	Use the 0, 30, 60 thresholds following shell.	SAC

12.9.7. Pharmacokinetic Tables

Pharmacokinetic: Tables					
No.	Population	IDSL / Example Shell	Title	Programming Notes	Deliverable [Priority]
PK Concentration					
4.1.	PK	PKCT1	Summary of Plasma GSK2330811 Concentration-Time Data	Note: LLQ=100 ng/mL. Values below LLQ have been imputed to 0. SD is set to missing if No. Imputed/n > 0.3 .	SAC
Derived PK parameters					
4.2.	PK	PKPT1	Summary of Derived Plasma Pharmacokinetic Parameters of GSK2330811		SAC
4.3.	PK	PKPT3	Summary of Log-Transformed Derived Plasma Pharmacokinetic Parameters of GSK2330811		SAC

CONFIDENTIAL

208564

12.9.8. Pharmacokinetic Figures

Pharmacokinetic: Figures					
No.	Population	IDSL / Example Shell	Title	Programming Notes	Deliverable [Priority]
PK Concentration					
4.1.	PK	PKCF1P	Individual GSK2330811 Plasma Concentration-Time Plot by Subject (Linear and Semi-Log)	Footnote for all PK and PK/PD figures: 'LLQ is calculated at 100 ng/mL. Values below LLQ have been imputed to 0.' Use actual time (days) as x axis (where days is a continuous variable)	SAC
4.2.	PK	PKCF4	Mean (\pm SD) Plasma GSK2330811 Concentration-Time Plots by Treatment (Linear and Semi-log)	Use planned time (days) as x axis (where days is a continuous variable)	SAC
4.3.	PK	PKCF5	Median (Range) Plasma GSK2330811 Concentration-Time Plots by Treatment (Linear and Semi-log)	Use planned time (days) as x axis (where days is a continuous variable)	SAC

CONFIDENTIAL

208564

12.9.9. Pharmacodynamic (and / or Biomarker) Tables

Pharmacodynamic (and or Biomarker): Tables					
No.	Population	IDSL / Example Shell	Title	Programming Notes	Deliverable [Priority]
Serum level of OSM					
6.1.	Safety	PD1	Summary of Serum Level of Free OSM by Treatment Group	Calculate confidence intervals and add number imputed Add footnote: [1] No. of subjects with BLQs assigned half of the lower limit of quantification (LLQ = 2.5pg/ml)	SAC
6.2.	Safety	PD1	Summary of Serum Level of Total OSM by Treatment Group	Calculate confidence intervals and add number imputed Add footnote: [1] No. of subjects with BLQs assigned half of the lower limit of quantification (LLQ = 2.5pg/ml)	SAC
6.3.	Safety	PD1	Summary of Ratio of Serum Level of Total OSM to Baseline by Treatment Group	Calculate confidence intervals and add number imputed Add footnote: [1] No. of subjects with BLQs assigned half of the lower limit of quantification (LLQ = 2.5pg/ml)	SAC
6.4.	Safety	PD2	Summary of Log Transformed Serum Level of Total OSM by Treatment Group	Calculate confidence intervals and add number imputed Add footnote: [1] No. of subjects with BLQs assigned half of the lower limit of quantification (LLQ = 2.5pg/ml)	SAC

CONFIDENTIAL

208564

Pharmacodynamic (and or Biomarker): Tables					
No.	Population	IDSL / Example Shell	Title	Programming Notes	Deliverable [Priority]
6.5.	Safety	PKPT1	Summary of Derived Serum Pharmacokinetic Parameters of Total OSM by Treatment Group		SAC
6.6.	Safety	PKPT3	Summary of Log-Transformed Derived Serum Pharmacokinetic Parameters of Total OSM by Treatment Group		SAC

CONFIDENTIAL

208564

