4.4. Scientific Rationale for Study Design

The proposed 450 mg single SC dose in Japanese participants is anticipated to result in exposure comparable to the 6 mg/kg (average 417 mg, range 375-443 mg) single SC dose tested in Caucasian participants in the FTIH study 201246 allowing a comparative assessment of ethnic sensitivity in terms of safety, tolerability and PK and PD in a Japanese population. Furthermore, a dose of 450 mg SC aligns with the highest anticipated dose to be administered in the global clinical studies with GSK2330811.

In addition, this study will be conducted in healthy male participants for the following reasons:

- Patients with inflammatory and fibrotic diseases may have existing comorbidities or be taking concomitant medications that may confound the analysis.
- It is anticipated that patients would derive little or no benefit from a single dose of GSK2330811, but that taking part in the study might interfere with their ability to receive other potentially efficacious therapies.
- Animal reproductive toxicity studies have not yet been carried out with GSK2330811 and therefore the benefit-risk of enrolling women of child-bearing

potential in this study, where they are unlikely to derive any direct benefit from a single dose of GSK2330811, does not support their inclusion. Moreover, enrolling only male participants will facilitate comparison with data from study 201246, a single-dose FTIH study of GSK2330811 in predominantly male Caucasian participants [Reid, 2018].

This study will include a placebo arm to ensure that the treatment-attribution of adverse events (AEs) is appropriately blinded and to provide control data for the PD and safety laboratory assessments.

The duration of follow-up will be about 126 days, which will be approximately 5 half-lives of GSK2330811 (half-life of between 19 to 25 days) [GlaxoSmithKline Document Number 2016N284919_02, 2019].

Exploratory endpoints have been chosen to confirm target engagement and further investigate PK/PD relationships in the blood.

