The safety and tolerability of ascending single SC doses of GSK2330811 in the range of 0.1 mg/kg to 6 mg/kg were studied in study 201246. GSK2330811 at these doses was generally well tolerated in healthy participants. Reversible, dose-dependent decreases in platelet counts were observed from the 1 mg/kg to the 6 mg/kg dose levels with recovery evident between Days 28 to 35. A reduction in haemoglobin from baseline values was observed in the GSK2330811 6 mg/kg group with all participants returning to within the normal range by Day 133. Further details can be found in Section 5 of the IB [GlaxoSmithKline Document Number [2016N284919_02](#), 2019].

The effect of GSK2330811 on platelets and haemoglobin is anticipated to be comparable in Japanese and Caucasian participants, since average exposure and target engagement are predicted to be comparable in the two populations. At the 6 mg/kg (average 417 mg) dose studied in study 201246, median maximum target engagement (TE) was 90% in serum. Therefore, a dose of 450 mg SC is appropriate to investigate the saturated PK/TE relationship. Furthermore, a dose of 450mg SC is the highest dose to be administered in the global clinical studies with GSK2330811.

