10.1.2. Summary Measure

Descriptive statistics (n, arithmetic mean, standard deviation [SD], 95% CI, minimum, median and maximum) will be calculated for free and total OSM concentrations over time. Descriptive statistics (n, geometric mean and standard deviation [SD] on log scale, CVb%) will be calculated for log transformed total OSM concentration and ratio to baseline. Plots of individual, mean concentrations with SD and median concentrations with range for total OSM will be produced.

Total OSM parameters will be calculated by standard non-compartmental analysis according to current working practices and using the currently supported version of WinNonlin. All calculations of non-compartmental parameters will be based on actual sampling times. Total OSM, Cmax, Tmax, AUC(0-t), AUC(0-inf), %AUCex, t1/2, CL/V, Vss/V, tlast might be calculated with non-compartmental analysis, from the serum concentration-time data, as data permits.

Only data listing provided for TPO and EPO concentrations.

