Is NQ impacted Total OSM Parameters Rule Being Followed	
Yes, refer to SOP_314000. If one or more non-quantifiable (NQ) values occur in a profile before the first measurable concentration, they will be assigned a value of zero concentration. For linear plots, zero concentration value(s) before the first measurable concentration will be included in the plot. For log-linear plots, zero concentration value(s) before the first measurable concentration will be assigned a missing value. If a single NQ value occurs between measurable concentrations in a profile, the NQ should generally be omitted (set to missing) in the derivation of total OSM parameters, statistical analysis, and the individual subject plots.
 
If two or more NQ values occur in succession between measurable concentrations, the profile will be deemed to have terminated at the last measurable concentration prior to these NQs. For the purpose of individual subject plots, these NQs will be set to 0, and the subsequent measurable concentrations will be retained. For the derivation of total OSM parameters, these NQs and any subsequent measurable concentrations will be omitted (set to missing).
 
NQs which occur after the last measurable concentration will be omitted (set to missing) in the derivation of pharmacokinetic parameters and from the individual subject plots.
 
For the calculation of mean or median total OSM profiles. When estimating the mean or median value for the concentration at a given time point (i.e., descriptive mean or median curve), the following guidelines should be considered:
 
All NQ values will be set to zero except when an individual NQ falls between two quantifiable values, in which case it will be omitted from the calculation of mean or median profiles. Measurable concentrations which follow more than one consecutive mid-profile NQ will be omitted (set to missing). The mean/median value at a time-point where one or more samples have NQ values will be reported (in tabular or graphical fashion) even if the mean/median value is below the LLQ of the assay. For linear plots, zero concentration value(s) will be included in the plot. For log-linear plots, zero concentration value(s) will be assigned a missing value.
 
Zero mean or median values will be included in summary tables. In certain cases, the NQ values could be set to missing or to some other values (e.g., $\frac{1}{2}$ LLQ) with proper scientific justification(s). A reference line indicating LLQ will be included in plots.
 
It should be noted that a high proportion of NQ values may affect the standard deviation (SD); if more than 30% of values are imputed, then SD will not be displayed.

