12.6.2.2. Imputation of Missing Data for OSM Free and Total

Element	Reporting Detail
LLQ/2	
 • If data are missing due to readings being below the limits of quantification, then a value equivalent to LLQ/2 will be imputed. • If the readings are above the upper limit of quantification, the sample should be further diluted to be within the upper limit of quantification of the assay. The measured concentration should then be corrected for the additional dilution factor. • These values will be used for the computation of the change from baseline and for summaries, plots and analysis, if deemed applicable. • The number of data imputed will be highlighted in the summaries and figures, whereas listings will report the values as below LLQ. • The numeric values and LLQ will be presented in listing as a reference, and the LLQ will be mentioned in footnotes where appropriate (e.g. figures).

CONFIDENTIAL

208564

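### Free OSM has no listed baseline-referenced display and no figure in the SAP, and the confidence interval in its one summary table rests on a below-LLQ constant with no suppression rule

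*SAP*

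**What the plan says.** **Protocol.** Section 8.6.1 names free and total OSM in serum as the means of assessing target engagement. Section 4.4 states the purpose: "Exploratory endpoints have been chosen to confirm target engagement". Section 4.5 reports that at the comparison dose in Study 201246 "median maximum target engagement (TE) was 90% in serum". Section 9.4.4 plans graphs over time for both free and total OSM.

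**SAP statistics.** Section 10.1.2 plans the count, mean, SD, 95% CI, median and extremes, which "will be calculated for free and total OSM concentrations over time". A second set, on the log scale, "will be calculated for log transformed total OSM concentration and ratio to baseline".

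**SAP displays.** Section 12.9.9 gives free OSM one table, 6.1, "Summary of Serum Level of Free OSM by Treatment Group", with confidence intervals, the number imputed and a footnote on the LLQ of 2.5 pg/mL. The baseline-referenced table is 6.3, "Summary of Ratio of Serum Level of Total OSM to Baseline by Treatment Group". Figures 6.1 to 6.3 and the scatter plot 7.1 are all total OSM. Listing 30 includes free OSM but for the PK population, which by SAP section 3 requires an active dose.

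**Values below LLQ.** Section 12.6.2.2, for free and total OSM: "If data are missing due to readings being below the limits of quantification, then a value equivalent to LLQ/2 will be imputed". Section 12.4.4, written for total OSM, adds that "if more than 30% of values are imputed, then SD will not be displayed". Section 12.4.3 and Table 4.1 apply the same rule to drug concentration.

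**The concern.** Free OSM is the fraction that drug binding should lower. Judging how far it falls requires each participant's post-dose value set against his own pre-dose value. Free OSM is sampled pre-dose and at 13 post-dose times, yet no listed display makes that comparison. Absolute summaries in about 7 active and 3 placebo participants mix the drug effect with the spread in baseline levels.

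The second problem is the interval. Where most values at a visit are below LLQ, the mean, SD and CI largely describe the constant 1.25. An interval that is narrow for this reason reflects the assay limit, not precise knowledge of suppression. The sponsor already withholds the SD in this situation for drug and total OSM. No such rule is written for free OSM, where low post-dose values are to be expected, and none mentions the CI.

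**Working it through.** The documents give no figure for free OSM that could be reproduced. The probabilities in Protocol 9.2 concern AUC and do not enter here.

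**Inputs from the documents**
- LLQ = 2.5 pg/mL (Table 6.1 footnote), so the imputed constant is 2.5/2 = 1.25.
- 7 active and 3 placebo participants, with 6 and 2 evaluable (Protocol 4.2).
- 30% imputation threshold (SAP 12.4.3 and 12.4.4).
- 90% engagement in Study 201246 (Protocol 4.5).

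**Assumptions.** Baseline free OSM is not given; 10 to 40 pg/mL is shown. Post-dose free OSM is taken as lognormal with median 10% of baseline, CV 30% or 50%, independent between participants. Reading the 90% as a reduction in free OSM is itself an assumption.

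**1. Displays side by side**

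| | Free OSM | Total OSM |
|---|---|---|
| Absolute level | Table 6.1 | Table 6.2 |
| Ratio to baseline | none | Table 6.3 |
| Log scale | none | Table 6.4 |
| Derived parameters | none | Tables 6.5, 6.6 |
| Profiles over time | none | Figures 6.1 to 6.3 |
| Against drug concentration | none | Figure 7.1 |

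SAP 2.1 records only the unplanned interim analysis as a change from the protocol's analysis, so the missing free OSM figure is not declared.

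**2. The interval.** CI = mean ± t(0.975, n−1) × SD/√n.
- All 7 below LLQ: mean 1.25, SD 0, CI 1.25 to 1.25. The same holds for n = 6, 3 or 2.
- Six below LLQ and one at 3 pg/mL: mean (6 × 1.25 + 3)/7 = 1.50, SD 0.66, CI 0.89 to 2.11. With the six values known only to lie between 0 and 2.5, the sample mean itself can be anywhere from 3/7 = 0.43 to 18/7 = 2.57, a wider range than the CI.
- Six below LLQ and one at 5 pg/mL: mean 1.79, SD 1.42, CI 0.47 to 3.10, set by one observation and the constant.

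If the 30% rule covered free OSM, it would start at 3 of 7 (43%; 2 of 7 is 29%). As written it removes only the SD.

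**3. How likely is collapse?** p = Φ([ln 2.5 − ln(0.1 × baseline)]/σ), with σ = √ln(1 + CV²), and P(all 7) = p^7. The last two columns show the reduction implied by the imputed value, 1 − 1.25/baseline, and the reduction the data support, 1 − 2.5/baseline.

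| Baseline (pg/mL) | p; all 7 (CV 30%) | p; all 7 (CV 50%) | Imputed reduction | Supported: at least |
|---|---|---|---|---|
| 10 | 0.999; 99% | 0.974; 83% | 87.5% | 75% |
| 15 | 0.959; 75% | 0.860; 35% | 91.7% | 83.3% |
| 20 | 0.776; 17% | 0.682; 7% | 93.8% | 87.5% |
| 25 | 0.500; 0.8% | 0.500; 0.8% | 95% | 90% |
| 40 | 0.055; about 0 | 0.160; about 0 | 96.9% | 93.8% |

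At 25 pg/mL exact collapse is rare, but with p = 0.5 the chance that 4 or more of 7 are below LLQ is one half by symmetry.

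**4. What a ratio can show.** A 90% reduction is quantifiable without leaning on the constant only if baseline is at least 2.5/(1 − 0.90) = 25 pg/mL. Below that, a below-LLQ result supports only a bound under 90%.

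**The case against.** Several stronger readings are tempting, and the documents do not support them.

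- **That free OSM is reported only as means.** Median, minimum, maximum and number imputed are planned too. A zero-width interval would stand beside a count showing every value imputed and a footnote giving the rule. This safeguard is real, but it does not make the interval meaningful.
- **That free OSM is never referred to baseline.** SAP 12.6.2.2 foresees using the imputed values for change from baseline where applicable, and SAP 4.2.1 defines percent change. What is missing is a listed display that delivers it.
- **That target engagement is not assessed.** The protocol uses free and total OSM together, the endpoints are serum levels, and total OSM has a ratio to baseline, derived parameters and a plot against drug concentration. The documents do not rank free above total OSM. What is absent is an estimate of free OSM suppression.
- **That the result could simply be set beside the 90%.** The documents give no formula for that figure and do not say how below-LLQ values were treated in Study 201246.

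It can also be said that SAP 10.1.5 promises graphs where appropriate for every variable in 10.1.1, free OSM included, and that Listing 30 lets a reader work out each active participant's ratio. Both are true, but the display list contains no such figure and Listing 30 leaves out placebo, which Protocol 4.4 includes to provide control data for the PD assessments. Dropping the mean and CI goes further than the sponsor's own rule, which drops only the SD.

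**Conclusion.** The point holds in a limited form. Free OSM, one of two measures by which the protocol assesses engagement, has no listed baseline-referenced display and no figure, although Protocol 9.4.4 plans one and total OSM has both. The interval in Table 6.1 reflects the imputation constant when most values are below LLQ, and it has zero width when all are.

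A reader might infer that the interval will collapse. That is not established, because it depends on a baseline level the documents do not give. Under the stated assumptions collapse is likely at about 10 pg/mL or lower (83% to 99% at 10) and very unlikely at 25 pg/mL or higher (under 1%).

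Severity is minor: the endpoint is exploratory, no hypothesis is tested, and no primary or secondary conclusion depends on it.

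**What to change.** 1. **SAP 10.1.2 and 12.9.9.** Derive each participant's free OSM ratio to baseline, or percent reduction, at each visit. When the post-dose value is below LLQ, report the reduction as at least 100 × (1 − LLQ/baseline). Derive no ratio when baseline is below LLQ, and state how many participants this affects. Summarise the median and range by arm and visit, plus each participant's maximum reduction, marking any statistic that is a bound.
2. **Comparison with Study 201246.** Set the result beside the 90% only if that study defined engagement in the same way.
3. **Table 6.1.** Extend the 30% rule to free OSM, counting LLQ/2 values as imputed, and apply it to mean, SD and CI. Keep n, number below LLQ, median, minimum and maximum, showing any that fall below LLQ as <2.5.
4. **SAP 12.9.10.** Add the free OSM figure planned in Protocol 9.4.4.
5. **Listing 30.** List free OSM for the Safety population so that placebo values appear.

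The cost is one derived variable, one table, one figure and a change of listing population, with no new samples. The price is fewer statistics at heavily censored visits. In a placebo arm of 3, a single below-LLQ value (33%) would already trigger the rule. Below LLQ the new summary gives bounds, not estimates.

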12.9.10. Pharmacodynamic (and / or Biomarker) Figures

Pharmacodynamic (and or Biomarker): Figures					
No.	Population	IDSL / Example Shell	Title	Programming Notes	Deliverable [Priority]
Serum levels of OSM					
6.1.	Safety	PKCF1P	Individual Serum Level of Total OSM Concentration-Time Plot by Treatment (Linear and Semi-Log)	Add LLQ reference line Conditionally add ULQ reference line Page by treatment Total OSM: LLQ is calculated at 2.5pg/ml. Values below LLQ have been imputed to LLQ/2. Use actual time (days) as x axis (where days is a continuous variable) Add Footnote to indicate amount of imputed data.	SAC
6.2.	Safety	PKCF4	Mean (\pm SD) Serum Level of Total OSM Concentration-Time Plots by Treatment (Linear and Semi-log)	Add LLQ reference line Conditionally add ULQ reference line Use planned time (days) as x axis (where days is a continuous variable) Total OSM: LLQ is calculated at 2.5pg/ml. Values below LLQ have been imputed to LLQ/2.	SAC
6.3.	Safety	PKCF5	Median (Range) Serum Level of Total OSM Concentration-Time Plots by Treatment (Linear and Semi-log)	Add LLQ reference line Conditionally add ULQ reference line Use planned time (days) as x axis (where days is a continuous variable) Total OSM: LLQ is calculated at 2.5pg/ml. Values below LLQ have been imputed to LLQ/2.	SAC

CONFIDENTIAL

208564

12.9.11. Pharmacokinetic / Pharmacodynamic Figures

Pharmacokinetic / Pharmacodynamic: Figures					
No.	Population	IDSL / Example Shell	Title	Programming Notes	Deliverable [Priority]
OSM vs GSK2330811 concentration					
7.1.	PK	PKPD_F1	Scatter Plot of Total Serum OSM vs Plasma Concentration of GSK2330811	X axis: PK Page by visit Add LLQ reference lines for both Conditionally add ULQ reference line for total Footnotes: GSK2330811: LLQ is calculated at 100 ng/mL. Values below LLQ have been imputed to 0. Total OSM: LLQ is calculated at 2.5pg/ml. Values below LLQ have been imputed to LLQ/2.	SAC

CONFIDENTIAL

208564

12.9.12. ICH Listings

ICH: Listings					
No.	Population	IDSL / Example Shell	Title	Programming Notes	Deliverable [Priority]
Subject Disposition					
1.	Screened	ES7	Listing of Reasons for Screen Failure		SAC
2.	Enrolled	ES2	Listing of Reasons for Study Withdrawal		SAC
3.	Enrolled	BL1	Listing of Subjects for Whom the Treatment Blind was Broken		SAC
4.	Enrolled	TA1	Listing of Planned and Actual Treatments		SAC
Protocol Deviations					
5.	Enrolled	DV2	Listing of Important Protocol Deviations		SAC
6.	Enrolled	DV2	Listing of COVID-19 related Protocol Deviations		SAC
7.	Enrolled	IE3	Listing of Subjects with Inclusion/Exclusion Criteria Deviations		SAC
Populations Analysed					
8.	Enrolled	SP3	Listing of Subjects Excluded from Any Population		SAC
Demography					
9.	Enrolled	DM2	Listing of Demographic Characteristics		SAC
10.	Enrolled	DM9	Listing of Race		SAC
Prior and Concomitant Medications					
11.	Enrolled	CM3	Listing of Concomitant Medications		SAC

CONFIDENTIAL

208564

ICH: Listings					
No.	Population	IDS / Example Shell	Title	Programming Notes	Deliverable [Priority]
Exposure and Treatment Compliance					
12.	Enrolled	EX3	Listing of Exposure Data	Order by treatment, subject r. Include: Treamtent, Site ID/subjID, Start Datetime of Dose/Study day, Stop Datetime of Dose/Study day, Dose (this will be the cumulative dose) (eg450), Dose units, Root of administration, Number of injections	SAC
Adverse Events					
13.	Enrolled	AE8	Listing of All Adverse Events		SAC
14.	Enrolled	AE7	Listing of Subject Numbers for Individual Adverse Events		SAC
15.	Enrolled	AE2	Listing of Relationship Between Adverse Event System Organ Classes, Preferred Terms, and Verbatim Text		SAC
Serious and Other Significant Adverse Events					
16.	Enrolled	AE8CP	Listing of Serious Adverse Events		SAC
17.	Enrolled	AE14	Listing of Reasons for Considering as a Serious Adverse Event		SAC
18.	Enrolled	AE8CP	Listing of Adverse Events Leading to Withdrawal from Study / Permanent Discontinuation of Study Treatment		SAC

CONFIDENTIAL

208564

ICH: Listings					
No.	Population	IDSL / Example Shell	Title	Programming Notes	Deliverable [Priority]
Haematology					
19.	Enrolled	SAFE_L1	Listing of All Haematology Values and Changes from Baseline	See listing 23 in 201246. Report: Standard result, Change from baseline and Percent change from baseline. Do not flag CTCAE grades	SAC
20.	Enrolled	LB5	Listing of Laboratory Values of CTCAE Grade	Include Haematology and clinical chemistry laboratory data	SAC
21.	Enrolled	LB5	Listing of All Laboratory Data for Subjects with Any Value of Potential Clinical Importance	Include Haematology and clinical chemistry laboratory data	SAC
22.	Enrolled	LB14	Listing of Laboratory Data with Character Results		SAC
Urinalysis					
23.	Enrolled	UR2	Listing of Urinalysis Results		SAC
ECG					
24.	Enrolled	EG3	Listing of All ECG Values for Subjects with Any Value of Potential Clinical Importance		SAC
25.	Enrolled	EG5	Listing of Abnormal ECG Findings		SAC
Vital Signs					
26.	Enrolled	VS4	Listing of All Vital Signs Data for Subjects with Any Value of Potential Clinical Importance		SAC
Immunogenicity					
27.	Enrolled	IMM2	Listing of Immunogenicity Results		SAC

CONFIDENTIAL

208564

